### 6.5.2 Post-scan

- MRI scan information
- DICOM image files (deidentified) if available
- Device functionality
- Programming functionality
- AE and/or protocol deviation (if applicable)

### 6.6 1-Month follow-up visit

(In clinic, 1 month  $\pm$  10 days since MRI scan)

The following information will be collected at the 1-month follow-up visit:

- Programming functionality
- AE and/or protocol deviation (if applicable)

### 6.7 Unscheduled visit

Subjects may be asked or need to return to the clinic to assess various program parameters and stimulation coverage or undergo additional surgery. If this occurs, the following information will be recorded:

• Reason for visit

- Action taken
- Programming functionality (if applicable)
- AE and/or protocol deviation (if applicable)
- Additional surgery information (if applicable)

### 6.8 Additional surgery

Subjects may be asked to return to the clinic for an additional surgery to revise, replace, reposition, or explant the leads or IPG. If this occurs, the following information will be recorded:

- Reason for surgery
- Action performed
- Lead and IPG data (if applicable)
- AE and/or protocol deviation (if applicable)

### 6.9 Health care economic data

Not applicable.

### 6.10 Description of activities performed by Sponsor Representatives

Trained sponsor personnel may perform certain activities to ensure compliance to the investigational plan and may provide technical expertise.

Sponsor personnel may:

• Provide technical support to the Investigators during MRI scan, additional surgery, and programming

Sponsor personnel will not:

- Perform the informed consent process
- Practice medicine
- Provide medical diagnosis or treatment to subjects
- Discuss a subject's condition or treatment with a subject without the approval and presence of a health care practitioner
- Independently collect clinical investigational data

### 6.11 Subject study completion

When the subject's participation in the clinical study has been completed (at 1-Month Follow-Up), the subject will return to the medical care as per physician's recommendation.

### 6.12 Any known or foreseeable factors that may compromise the outcome

All foreseeable factors that may compromise the outcome of the clinical study or the interpretation of the results have been accounted for by clinical study design and well-defined subject selection criteria.

Subject recruitment and retention will be mastered throughout the study and include (but are not limited to) the following activities: evaluation of the site and Investigators, training of site personnel, developing site support materials, providing subject visit calendars.

A Clinical Events Committee (CEC) will be formed as best practice to ensure that the primary outcome is as free from bias as possible. The CEC will review and adjudicate reportable adverse events as defined in the CEC charter for seriousness, device-relatedness, and MRI-relatedness.

### 6.13 Description of the methods that will be used to address potentially confounding factors

Stratified analysis will be used to diagnose the potential confounding factors, and multiple regression will be used to adjust the outcome of the primary endpoint in case confounding factors are identified. The factors of interest can be, but are not limited to:

- Subject baseline characteristics
- Use of other medical devices

### 6.14 Criteria and procedures for subject withdrawal or discontinuation

Each subject should remain in the study until completion of the required follow up period; however, a subject's participation in the study may be discontinued at any time. Should this occur, the reason for discontinuation must be documented in the withdrawal form.

Subjects must be informed about their right to withdraw from the study at any time, and for any reason, without sanction, penalty, or loss of benefits to which the subject is otherwise entitled and that withdrawal from the study will not jeopardize their future medical care or relationship with the Investigator. Subjects will be asked to specify the reason for the termination but have the right not to answer.

The Investigator may decide to withdraw a subject from the study at any time with reasonable rationale. The subject's future care will not be influenced by a decision, voluntary or otherwise, to withdraw from the study. All reasonable efforts should be made to retain the subject in the clinical study until completion of the study.

Reasons for subject's withdrawal include, but are not limited to:

- Subject refuses to continue participating in the study
- Subject does not meet the inclusion/exclusion criteria and does not require additional followup for safety reasons.
- Subject is deceased (cause must be documented)
- Subject's non-compliance
- Subject's participation is terminated by the PI or Investigator, although the subject consented, since participation is no longer medically appropriate
- Subject is 'lost to follow up': Subject does not adhere to the scheduled follow up visits but has not explicitly requested to be withdrawn from the clinical study this does not apply to missed visits). Site personnel should make all reasonable efforts to locate and communicate with the subject to achieve subject compliance to the scheduled follow up visits:
  - A subject will be considered 'Lost to Follow Up' after a minimum of 2 phone calls of a physician or delegate at the investigational site to the subject or contact. These 2 phone calls need to be documented in the subject's hospital records.
  - If these attempts are unsuccessful, a letter should be sent to the subject's last known address or general practitioner (GP) and a copy of this letter should be maintained in the subject's hospital records.

### **Clinical Investigation Plan**

If a subject withdraws from the clinical study, the site will record the subject's reasons for withdrawal on a Withdrawal CRF.

No additional follow-up will be required or data recorded from subjects once withdrawn from the clinical investigation.

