### 8.1.3 Serious Adverse Event (SAE)

An adverse event that led to:

- Death
- A serious deterioration in the health of the subject, that either resulted in:
  - A life-threatening illness or injury OR
  - A permanent impairment to a body structure or a body function OR
  - An in-subject or prolonged hospitalization OR
  - A medical or surgical intervention to prevent life-threatening illness or injury or permanent impairment to a body structure or a body OR
- Fetal distress, fetal death, or a congenital abnormality or birth defect
- Malignant tumor

Note: A planned hospitalization for a pre-existing condition, or a procedure required by the CIP is not considered a serious adverse event.

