### 8.2 Procedure for assessing, recording and reporting AEs, ADEs, SADEs:

Safety surveillance within this study and the safety reporting, both performed by the Investigator, starts as soon as the subject is enrolled in this study (date of signature of the informed consent). The safety surveillance and the safety reporting will continue until the last study visit has been performed, the subject is deceased, the subject/Investigator concludes his participation in the study or the subject/Investigator withdraws the subject from the study.

Records related to the subject's subsequent medical course must be maintained and submitted (as applicable) to the Sponsor until the event has subsided or, in case of permanent impairment, until the event stabilizes and the overall clinical outcome has been ascertained. Adverse events will be monitored until they are adequately resolved. The status of the subject's condition should be documented at each visit.

Adverse event data will be collected throughout the clinical study and will be reported to the Sponsor on a dedicated case report form.

Reportable events to sponsor are considered:

- 1. All Serious Adverse Events
- 2. All procedure- (e.g., MRI scan) or device-related Adverse Events (whether or not the event is considered serious).

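### Sections 6.14 and 8.2 give conflicting instructions for an adverse event still open when a subject withdraws, so its outcome, and sometimes its seriousness and adjudication, can be lost

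*Combined protocol and SAP*

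**What the plan says.** Section 6.14 closes with a rule that covers every type of withdrawal: "No additional follow-up will be required or data recorded from subjects once withdrawn from the clinical investigation". It makes no exception for an adverse event in progress.

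Section 8.2 contains two rules.

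- Its first paragraph sets the period of safety surveillance and reporting. Among the stopping points is when "the subject/Investigator concludes his participation in the study or the subject/Investigator withdraws the subject from the study". This agrees with 6.14.
- Its second paragraph deals with events already known. "Records related to the subject's subsequent medical course must be maintained and submitted (as applicable) to the Sponsor until the event has subsided", or, for permanent impairment, until the event is stable and its outcome established. It adds: "Adverse events will be monitored until they are adequately resolved". No exception is made for withdrawn subjects.

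Three other provisions depend on what happens after onset. Section 8.1.3 includes among its seriousness criteria "A permanent impairment to a body structure or a body function". Section 6.12 gives the CEC its task: "The CEC will review and adjudicate reportable adverse events as defined in the CEC charter for seriousness, device-relatedness, and MRI-relatedness". Table 3 in section 8.2 lists MRI effects that need no report unless they worsen or outlast a stated window.

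**The concern.** A site with a withdrawn subject and an unresolved event cannot satisfy both 6.14 and the second paragraph of 8.2. The first bars recording the outcome and the second requires it. The plan states no order of precedence, and up to 30 centers may decide differently, so the CEC could receive complete information on one event and truncated information on a similar one.

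Safety is the study's only primary objective. What is at stake is mainly the description of events: how they ended, whether they met a seriousness criterion that only time can establish, and whether relatedness could be judged on full information. A secondary stake is the primary count, in the few cases where being counted depends on what happens after withdrawal.

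**Working it through.** **Step 1. The rules side by side, for an event open at withdrawal**

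| Source | Follow-up of the event | Recording and submitting data |
|---|---|---|
| 6.14, closing sentence | Not required | None |
| 8.2, first paragraph | Surveillance ends | Reporting ends |
| 8.2, second paragraph | Continues to resolution | Required, as applicable, until subsided or stable |

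One might read the first paragraph of 8.2 as ending the search for new events and the second as governing known ones. That would reconcile 8.2 with itself. It would not reconcile 8.2 with 6.14, which stops all data recording and not only the detection of new events.

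**Step 2. What is lost if 6.14 is applied**

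- Outcome: lost for any event unresolved at withdrawal.
- Seriousness: lost only where permanence, shown later, is the sole qualifying criterion. Hospitalization, or intervention to prevent permanent impairment, also makes an event serious under 8.1.3 and may be evident at once.
- CEC adjudication: made on whatever was known at withdrawal.

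**Step 3. Does the primary count change?**

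Section 12.1 counts subjects with an MRI scan-related event. Seriousness does not enter. Section 8.2 makes scan-related events reportable whether serious or not, and reporting begins at consent. An event recorded as scan-related before withdrawal therefore already counts. Two routes remain:

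1. MRI-relatedness is still undetermined at withdrawal and later information would have settled it.
2. A Table 3 event is inside its window at withdrawal and later persists or worsens. The windows are: during the scan (claustrophobia); during the scan and under 1 hour after (sweating, bodily warmth, pocket warmth); under 24 hours (hearing); under 48 hours (stiffness).

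Section 12.8 does not name scanned subjects who withdraw among its examples of exclusions, and 12.9 allows no imputation. On either route the subject would probably be analysed as event-free. That is an inference; the plan does not say so.

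**Step 4. The plan's own figure**

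Inputs from 12.1 and 12.2: goal 10%, assumed rate 1%, one-sided 5%, 80% power, Clopper-Pearson bound, 46 scanned. The one-sided 95% upper bound U for x events in n solves P(X ≤ x | n, U) = 0.05.

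- At a true rate of 10%: P(X ≤ 1) = 0.9^46 + 46 × 0.1 × 0.9^45 = 0.0079 + 0.0401 = 0.0480, so one event passes.
- Power at 1%: 0.99^46 + 46 × 0.01 × 0.99^45 = 0.6298 + 0.2926 = 0.922. At n = 45 only zero events pass, and power is 0.636. So 46 is the smallest exact size with at least 80% power, and the plan's figure reproduces.
- Enrollment: 46/0.95 = 48.4, rounded up to 49.

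**Step 5. Leverage of one lost event**

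| Events in 46 | One-sided 95% upper bound | Result against 10% |
|---|---|---|
| 0 | 6.3% | pass |
| 1 | 9.9% | pass |
| 2 | 13.1% | fail |
| 3 | 16.0% | fail |

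Losing one event takes 1 to 0 (pass either way), 2 to 1 (fail becomes pass) or 3 to 2 (fail either way). The result changes only when the true total is two. P(X = 2) = 1035 × p² × (1 − p)^44, where 1035 = 46 × 45/2. At the plan's p = 1% this is 1035 × 0.0001 × 0.6426 = 6.7%. At p = 10% it is 10.0%. Its maximum, at p = 2/46, is 27.7%. These are ceilings: one of the two events must also be lost by a route in step 3. The same cut-off of one event applies for 46 to 49 subjects analysed.

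**The case against.** The strongest reply is that the text can be read coherently. The second paragraph of 8.2 is the more specific rule for known events, and 6.14 says that follow-up is not required, which does not forbid it. Section 6.14 lists ineligible subjects for withdrawal only if they need no further safety follow-up, and it asks sites to make reasonable efforts to retain subjects. This explains how a careful site might act. It does not settle the matter: the data-recording half of 6.14 is unconditional, and the safety qualifier is attached to ineligible subjects only, not to refusal, non-compliance or termination by the investigator.

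Stopping data collection at withdrawal is also a common way to respect consent. That stands for a subject who refuses further contact, and no wording will recover that subject's data. It does not explain a data stop when the investigator ends participation of a subject who still consents.

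A reader might infer that a subject who leaves because of a scan event drops out of the primary endpoint, or that a frozen seriousness grade moves the confidence bound. The documents do not support either. The event would be reportable before withdrawal, the reason for leaving goes on the withdrawal form unless the subject declines to give it, and the endpoint ignores seriousness.

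A reader might also infer that the loss is informative because events drive withdrawal. That is plausible but not documented. The only dropout figure, about 5%, covers enrollment to scan, and no rate after the scan is given.

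**Conclusion.** The contradiction is real and nothing in the plan resolves it. Its main effect is on event outcome, on seriousness that rests on later-proven permanence, and on the completeness of CEC adjudication. The primary count is exposed only through undetermined MRI-relatedness or a Table 3 event open at withdrawal, and the latter requires formal withdrawal within at most 48 hours of the scan.

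It would be too strong to say that one such event decides the trial. It does so only if the true total is two, which has probability 6.7% at the plan's assumed 1% rate and at most 27.7% at any rate, before allowing for the chance that the event is actually lost.

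This rests on 46 subjects analysed, the one-sided 95% bound implied by 12.2, and withdrawn scanned subjects being kept in the denominator. How often an event will be open at withdrawal is unknown and probably rare. The point is a worthwhile correction to a safety study, not a threat to its design.

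**What to change.** Reconcile 6.14 with both paragraphs of 8.2.

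- In 6.14, state that withdrawal ends study visits and device checks, but that an adverse event or Table 3 event open at withdrawal is followed for outcome under the second paragraph of 8.2, with the subject's agreement, by telephone or from medical records.
- Record the outcome on the adverse event form and make it available to the CEC. For a Table 3 event, record whether it worsened or outlasted its window.
- If the subject declines, record the refusal.
- Put the same exception in the first paragraph of 8.2, so that the end of surveillance for new events does not end follow-up of known ones.

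The cost is a short amendment, matching consent wording and probably a few extra contacts over the whole study. Sample size, endpoint and visit schedule do not change. Subjects who refuse contact will still have unknown outcomes, but these will be visible as such.

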### 7.0 COMPLIANCE TO CIP

#### 7.1 Statements of compliance

The study will be performed in accordance with the most current versions of the World Medical Association (WMA) Declaration of Helsinki, and any regional and/or national regulations as appropriate.

The current version of the harmonized ISO14155 shall be used as a guideline.

The Investigator will not start enrolling subjects or requesting informed consent from any subject prior to obtaining IRB/EC approval and Competent Authority approval, if applicable, and authorization from the sponsor in writing for the study.

In case additional requirements are imposed by the IRB/EC or Competent Authority, those requirements will be followed, if appropriate. If any action is taken by an IRB/EC, and regulatory requirements with respect to the study, that information will be forwarded to Abbott.

As sponsor, Abbott has taken up general liability insurance in accordance with the requirements of the applicable local laws.

If required, additional subject coverage or a study specific insurance will be provided by the Sponsor as well.

### 7.2 Adherence to the Clinical Investigation Plan

A deviation is defined as an event where the clinical Investigator, site personnel, sponsor or sponsor representative did not conduct the clinical study according to the Clinical Investigational Plan, IRB/EC requirements, or the Investigator Agreement. The Investigator is not allowed to deviate from the CIP, except as specified under emergency circumstances.

In some cases, failure to comply with the CIP may be considered failure to protect the rights, safety and well-being of subjects, since the non-compliance exposes subjects to unreasonable risks. For example, failure to adhere to the inclusion/exclusion criteria: these criteria are specifically defined by the Sponsor to exclude subjects for whom the device is not beneficial and use involves unreasonable risks. This may be considered failure to protect the rights, safety, and well-being of the enrolled subject. Similarly, failure to perform safety assessments intended to detect adverse events may be considered failure to protect the rights, safety and well-being of the enrolled subject. Investigators should seek minimization of such risks by adhering to the CIP.

Simultaneously, in the event that adhering to the CIP might expose the subject to unreasonable risks, the Investigator is also required to protect the rights, safety, and well-being of the subject by

## **Clinical Investigation Plan**

intentionally deviating from the requirements of the CIP so that subjects are not exposed to unreasonable risks.

It is the responsibility of the Investigator to provide adequate medical care to a subject enrolled in an investigation.

Regulations require that the PI maintain accurate, complete, and current records, including documents showing the date of, and reason for, every deviation from the Clinical Investigational Plan. Relevant information for each deviation will be documented on a Deviation Case Report Form. The site will submit the CRF to Abbott.

Regulations require Investigators obtain approval from Abbott and the IRB/EC (as required) before initiating changes in or deviations from the protocol, except when necessary to protect the life or physical well-being of a subject in an emergency.

Prior approval must be requested when the PI anticipates, contemplates, or makes a conscious decision to depart from the CIP, except when unforeseen circumstances are beyond the Investigator's control (e.g. a subject who fails to attend a scheduled follow-up visit, a subject is too ill to perform a CIP-required test, etc.). All deviations, including those beyond the Investigator's control, must be reported on a CRF.

To obtain approval, the Principal Investigator may call or email and discuss the potential deviation with Abbott or designee prior to initiating any changes.

All deviations must be reported to appropriate regulatory authorities in specified timelines (if appropriate).

The Investigator is required to adhere to local regulatory requirements for reporting deviations to IRB/EC.

### 7.3 Repeated and serious non-compliance

In the event of repeated non-compliance or a one-time serious non-compliance, as determined by the Sponsor, a Clinical Research Associate or clinical representative will attempt to secure compliance by one or more of the following actions:

- Visiting the Investigator
- Contacting the Investigator by telephone
- Contacting the Investigator in writing
- Retraining of the Investigator

If an Investigator is found to be repeatedly non-compliant with the signed agreement, the CIP or any other conditions of the clinical study, the Sponsor will either secure compliance or, at its sole discretion, terminate the Investigator's participation in the clinical investigation.

### 8.0 ADVERSE EVENT, ADVERSE DEVICE EFFECT

### 8.1 Definitions

### 8.1.1 Medical device

Any instrument, apparatus, machine, appliance, implant, software, material, or other similar or related article:

- Intended by the manufacturer to be used, alone or in combination, for human beings for one or more of the specific purpose(s) of
  - Diagnosis, prevention, monitoring, treatments or alleviation of disease
  - o Diagnosis, monitoring, treatment, alleviation of, or compensation for, an injury
  - Investigation, replacement, modification, or support of the anatomy or of a physiological process
  - Supporting or sustaining life
  - Control of conception
  - Disinfection of medical devices
- Which does not achieve its primary intended action in or on the human body by pharmacological, immunological, or metabolic means, but which may be assisted in its intended function by such means.

### 8.1.2 Adverse Event (AE)

An adverse event (AE) is any untoward medical occurrence, unintended disease or injury, or untoward clinical signs (including abnormal laboratory findings) in subjects, users, or other persons, whether or not related to the medical device under study.

Note 1: This definition includes events related to the medical device under study.

Note 2: This definition includes events related to the procedures involved.

**Note 3:** For users or other persons, this definition is restricted to events related to medical devices under investigation.

### 8.1.3 Serious Adverse Event (SAE)

An adverse event that led to:

- Death
- A serious deterioration in the health of the subject, that either resulted in:
  - A life-threatening illness or injury OR
  - A permanent impairment to a body structure or a body function OR
  - An in-subject or prolonged hospitalization OR
  - A medical or surgical intervention to prevent life-threatening illness or injury or permanent impairment to a body structure or a body OR
- Fetal distress, fetal death, or a congenital abnormality or birth defect
- Malignant tumor

Note: A planned hospitalization for a pre-existing condition, or a procedure required by the CIP is not considered a serious adverse event.

